#### Death

If a participant dies due to MS, it will be considered a confirmed disability progression regardless of the baseline EDSS or the change in EDSS. The time to event will be calculated as

- (date of EDSS assessment at a tentative onset of disability progression date of randomization + 1), or
- (date of death date of randomization + 1) if a tentative onset date does not exist.

If a participant dies for other reasons before a 6-month CDP, the participant's event time will be censored at the date of last EDSS assessment.

#### **Analytical Approach**

The time to onset of 6-month CDP will be modeled by a Cox proportional hazards model with robust variance estimation (1). The covariates included in the model are treatment group, age at screening (>40,  $\leq$ 40), region (US, non-US), baseline EDSS score and baseline gadolinium (Gd)-enhancing T1 lesions (present, absent). The hazard ratio, its 95% confidence interval and the p-value for comparing tolebrutinib to placebo will be estimated from this model. Comparison between tolebrutinib and placebo will also be assessed by a log-rank test stratified by age at screening (>40,  $\leq$ 40 years) and region (US, non-US). Kaplan-Meier (KM) plots of the cumulative incidence rate will be provided by treatment group to depict the course of onset of 6-month CDP over time. The proportion of participants with events at given time points (eg, Months 6, 12, 18, 24, 30, ...) and median time to 6-month CDP will be calculated using the KM estimates.

#### 3.2.3 Multiple imputation for missingness due to end of study

For participants who meet 3-month CDP criteria, and continue to meet the criteria for EDSS disability progression through the final study assessment, but do not reach 6-month confirmation, the 6-month CDP event status (ie, confirmed or not confirmed) of the participant will be determined by a logistic regression model as follows:

$$Y_i \sim Bernoulli(p_{ij}), i = 1, ..., n_j; j = 1, 2$$

$$logit(p_{ij}) = ln\left(\frac{p_{ij}}{1 - p_{ij}}\right) = \beta_{0j} + \beta_{1j}x_{1ij} + \beta_{2j}x_{2ij} + \beta_{3j}x_{3ij} + \beta_{4j}x_{4ij}$$

where  $Y_{ij}$  is the indicator for event status for participant *i* from group *j*; 1 = 6-month CDP, 0 = no 6-month CDP,  $p_{ij}$  is the probability that participant *i* from group *j* with a 3-month CDP has a 6-month CDP event,  $x_{1ij}$  is the age at screening (>40, <40 years),  $x_{2ij}$  is the geographic region (US, non-US),  $x_{3ij}$  is the baseline EDSS score,  $x_{4ij}$  is baseline Gd-enhancing T1 lesions (present, absent), and  $\beta_{kj}$  are the model parameters (k = 0,1,2,3,4; j = 1,2). The logistic model parameters  $\beta_{kj}$  will be estimated from participants with a 3-month CDP and who do not have missing value due to end of study. Separate logistic models will be estimated within each treatment arm. Then, these estimates will be used to calculate the predicted probability for participants who meet 3-month CDP criteria and continue to meet criteria for EDSS disability

Statistical Analysis Plan SAR442168-EFC16645 - tolebrutinib 30-Apr-2024 Version number: 3

progression through the final study assessment, and missingness due to end of study. Finally, the missing value for participants with an initial onset of disability progression and missingness for 6-month CDP due to end of study will be imputed via a randomly generated value from a Bernoulli distribution with  $p_{ij}$ .

Using the above methodology, 1000 complete data sets will be generated with imputed missing data via PROC MI in SAS®. Each of the data sets will be analyzed using the Cox proportional hazards model as described above. Log-rank test and KM plot will also be provided based on 1000 complete data sets based on the method in (2). The SAS MIANALYZE procedure will be used to generate statistical inferences by combining results from the 1000 analyses using Rubin's formula.

Sample SAS code is provided below:

```
proc mi data=DATAIN out=DATAOUT seed=16645 nimpute=1000;
by Treatment_group;
var age_strata geographic_region EDSS_base Gd_T1;
fcs logistic (Confirmation = age_strata geographic_region EDSS_base Gd_T1/
link=glogit);
run;
PROC MIANALYZE data= DATAOUT;
modeleffects Estimate;
stderr StdErr;
run;
```

DATAIN only includes participants who meet the imputation criteria mentioned above. Details of multiple imputation can be found in SAS support document (3).

#### 3.2.4 Sensitivity analysis

The following sensitivity analyses, without any imputation, will be performed to evaluate the impact of missing data to the primary analysis results:

- 1. Participants with a potential onset of disability progression but without 6-month confirmation due to missing data, regardless of reason, will be considered to have confirmed progression with the time to onset being the time to the initial EDSS increase. Of note, a potential onset is invalidated if there is any non-confirmatory EDSS in the confirmation period that does not meet the minimum change required for progression.
- 2. Participants with missing or incomplete 6-month CDP will be treated as censored at the last EDSS assessment date.

For the above analyses, the same Cox proportional hazards model as described in Section 3.2.2, without imputation, will be used to estimate the hazard ratio, 95% CI, and p-value on tolebrutinib compared to placebo.

#### 3.2.5 Subgroup analyses

To assess the homogeneity of the treatment effect across various subgroups, analyses will be performed on the primary endpoint across the following (no subgroup analysis will be performed if fewer than 5 participants in one category):

- Geographic region (US, non-US; Eastern Europe, Western Europe, North America, rest of the world [ROW])
- Age at screening (>40,  $\leq$ 40 years)
- Sex (Male or Female)
- Race (White, Black or African American, Asian, Other).
- Baseline Gd-enhancing T1 lesions (present, absent)
- Baseline EDSS score ( $\leq 4.5, >4.5; \leq 5.5, >5.5$ )
- Prior disease modifying therapy use  $(0, 1, \geq 2)$
- Duration since relapsing-remitting multiple sclerosis (RRMS) symptom onset (≤5, >5 to ≤10, >10 years)
- Adjudicated relapse during the study (yes, no)

Since adjudicated relapse during the study is a post randomization event, this subgroup analysis is purely exploratory.

The treatment effect (tolebrutinib compared to placebo) for the primary endpoint will be provided, as well as the corresponding 95% CI, for each subgroup separately, using the same methods as described in Section 3.2.2. Forest plots of hazard ratios and the corresponding 95% CIs will be provided.

Treatment by subgroup interaction and its p-value will be derived from a Cox proportional hazards model with terms for treatment group, age at screening (>40,  $\leq$ 40), region (US, non-US), baseline EDSS score, baseline Gd-enhancing T1 lesions (present, absent), subgroup (if different than the aforementioned covariates) and treatment by subgroup interaction as covariates. If quantitative treatment by subgroup interaction is detected with nominal p-value <0.1 for any subgroup factor, a further investigation will be performed to evaluate possible qualitative interaction.

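### SAP 3.2.5 admits subgroups by number of participants, not events, and the robust-variance intervals it then reports are too narrow in sparse categories

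*SAP*

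**What the plan says.** - **Threshold.** SAP 3.2.5 sets one condition: "no subgroup analysis will be performed if fewer than 5 participants in one category". No minimum number of events is given, overall or per arm.
- **Method.** The treatment effect and 95% CI are produced "for each subgroup separately, using the same methods as described in Section 3.2.2". The Analytical Approach in SAP 3.2.2 defines this as a "Cox proportional hazards model with robust variance estimation". Its terms are treatment, age group, region, baseline EDSS and baseline Gd status, so each fit has five parameters.
- **Interaction.** SAP 3.2.5 writes this model out separately: "Treatment by subgroup interaction and its p-value will be derived from a Cox proportional hazards model with terms for treatment group", followed by the covariates, the subgroup and the product term. It names no variance estimator. Further investigation follows if an "interaction is detected with nominal p-value <0.1 for any subgroup factor".
- **What is absent.** There is no small-sample correction, no penalised likelihood and no rule for an arm without events. Protocol 9.4.2 leaves subgroup details to the SAP.

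**The concern.** How well a hazard ratio is estimated depends on events, and five participants carry about one event here. Normally a weak threshold does little harm, because a sparse category shows a very wide interval and readers discount it. The sandwich estimator removes that protection.

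If one arm has no events, the log hazard ratio runs off to plus or minus infinity. The information for treatment shrinks towards zero, so the model-based standard error explodes, which is the right signal. The score residuals in the middle of the sandwich shrink at the same rate, so the robust standard error stays moderate. The forest plot for the primary endpoint would then show an extreme hazard ratio with a tight interval excluding 1, in a category with almost no information.

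**Working it through.** **Inputs (SAP section 4):** 288 events, hazard ratio 0.70, 2:1 allocation, two-sided alpha 0.05, 23.6% placebo events at 2 years, 10% annual discontinuation, 24 months' accrual, 24 months' minimum follow-up.

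**The plan's own figure.** Schoenfeld: √(288 × (2/3)(1/3) × (ln 0.70)²) − 1.96 = 2.853 − 1.96 = 0.893, giving power 0.814. The stated 80% is reproduced.

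**Event probability per participant.** Placebo hazard λ = −ln(1 − 0.236)/2 = 0.1346 per year; tolebrutinib 0.70 × 0.1346 = 0.0942; dropout δ = −ln(0.90) = 0.1054. With follow-up T uniform on 2 to 4 years, P(event) = λ/(λ+δ) × (1 − E[exp(−(λ+δ)T)]).
- Placebo: 0.561 × (1 − 0.4915) = 0.285.
- Tolebrutinib: 0.472 × (1 − 0.5532) = 0.211.
- Average at 2:1: (2 × 0.211 + 0.285)/3 = 0.236. Times 1290 this gives 304 events, in line with the 288 target.

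**At the threshold.** Five participants expect 5 × 0.236 = 1.2 events, and P(no event) = 0.764⁵ = 0.26.

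**Chance that only one arm has events.** For n participants this is (1 − 0.211 × 2/3)ⁿ + (1 − 0.285/3)ⁿ − 2 × 0.764ⁿ. At n = 10: 0.220 + 0.369 − 2 × 0.068 = 0.45.

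**Simulation.** The five-term model was fitted within a category, with a true homogeneous hazard ratio of 0.70. Assumptions not in the documents: 85% aged over 40, 15% US, 12% Gd present, covariates without effect on the hazard. Hazards were constant, there was no multiple imputation, and separated fits were reported.

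| n | Expected events | P(events in one arm only) | Robust coverage | Model-based coverage |
|---|---|---|---|---|
| 5 | 1.2 | 0.55 | 0.15 | 0.78 |
| 10 | 2.4 | 0.45 | 0.28 | 0.93 |
| 15 | 3.5 | 0.29 | 0.48 | 0.97 |
| 20 | 4.7 | 0.18 | 0.69 | 0.97 |
| 30 | 7.1 | 0.06 | 0.87 | 0.96 |
| 40 | 9.4 | 0.02 | 0.93 | 0.96 |
| 60 | 14.1 | 0.003 | 0.94 | 0.95 |
| 120 | 28.3 | about 0 | 0.95 | 0.95 |

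Repeated simulations gave robust coverage of 0.28 to 0.35 at n = 10, 0.66 to 0.72 at 20, 0.83 to 0.87 at 30 and 0.91 to 0.95 at 45. The spread at n = 10 exceeds simulation error (about 1 point), so the smallest sizes indicate order of magnitude only.

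- **One arm without events:** robust standard error about 0.5 to 1.3, model-based in the thousands. The robust interval covered the true value in 0 to 12% of such fits.
- **Excluding 1:** the robust interval did so in 70% of categories at n = 10 and 33% at n = 20, against 5% and 4% with model-based variance.
- **Not only overfitting:** with treatment alone in the model, robust coverage is still 0.46, 0.80 and 0.92 at n = 10, 20 and 30.

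**Interaction test, if robust variance were used there.** With 1290 participants, one small category, no true interaction and nominal level 0.10, rejection rates (robust against model-based) were 0.52 against 0.03 for a category of 10, 0.21 against 0.03 for 20, 0.17 against 0.09 for 30, and 0.11 against 0.09 for 60. Simulation error is 2 to 3 points.

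**The case against.** The strongest objection concerns reach. The documents give no category sizes. With 1100 to 1290 randomized, a factor such as sex is far above the affected range. A reader might infer that non-White race categories, RRMS onset within 5 years or relapse during the study are sparse. That is plausible, but the documents do not establish it, and SAP 3.2.5 already labels the relapse subgroup as exploratory only. This objection stands and limits the point to sparse categories, whichever they turn out to be.

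Second, much of the lost coverage comes from separated fits, which an analyst would probably notice from the absurd point estimate. If separated or non-converged fits were dropped, robust coverage at n = 15 to 30 would be 0.91 to 0.93. This stands in part: the SAP has no rule to drop them, and what remains is still somewhat low.

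Third, the imported method includes the imputation of SAP 3.2.3. If imputed status moved an arm between zero and one event, between-imputation variance would widen the interval. This was not quantified.

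Fourth, the threshold might mean 5 per arm, or about 15 in total at 2:1. Robust coverage at 15 is still about 0.48.

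**Conclusion.** The point holds for sparse categories. Under the planning assumptions, the nominal 95% interval prescribed by SAP 3.2.5 is materially too narrow below roughly 45 participants (45 × 0.236, or about 10.6 events) and close to nominal by 45 to 60. The result rests on the assumed covariate prevalences, constant hazards, no imputation, and separated fits being reported.

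Three stronger readings are tempting but not supported:
- **That the subgroup intervals are wrong in general.** At n = 120, robust and model-based coverage are both 0.95.
- **That the plan builds in false interaction signals.** SAP 3.2.5 imports the 3.2.2 method for the effect and CI within each subgroup. Its separate interaction model names no variance estimator, and with model-based variance the test is conservative in the smallest categories. The defect there is silence on the estimator.
- **That the trial's conclusion is at risk.** No subgroup result enters the hierarchy in SAP 3.5, and the primary test uses the whole ITT population.

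What remains is a prespecified rule that can print misleadingly precise results in the least informative rows of the primary endpoint's consistency display. It is worth correcting before unblinding.

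**What to change.** Change SAP 3.2.5 in two places.

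1. **Variance.** State that subgroup hazard ratios and CIs use model-based or profile-likelihood variance, and that the interaction test uses the same. Model-based variance is the simpler choice, because SAP 3.2.3 combines estimates and standard errors by Rubin's formula. It does most of the work: over a mix of sizes from 5 to 80, coverage is 0.943 against 0.695 with robust variance under the current rule.
2. **Threshold.** Replace the 5-participant rule with an event rule, for example at least 10 events in total and at least 2 to 3 in each arm. Otherwise show only participants and events by arm. With at least 10 events and 3 per arm, coverage over the same mix is 0.957 robust and 0.959 model-based. One event per arm is not enough if robust variance is kept (0.833).

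The model terms and race categories can stay as they are. Switching models between rows or pooling categories would make the forest plot harder to compare across rows, and Protocol 10.1.4 plans primary-endpoint analyses by race.

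The cost is SAP wording only. Some small categories will show counts in place of a hazard ratio. The primary analysis, alpha and sample size do not change.

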#### 3.3 SECONDARY ENDPOINT(S) ANALYSIS

The secondary endpoints detailed in this section are for assessing efficacy of tolebrutinib compared to placebo. Other secondary endpoints analyses are defined in Section 3.6.2 (AE, SAE), Section 3.6.3.1 (laboratory abnormalities), Section 3.7.1.1 (PK) and Section 3.7.2 (PD).

#### 3.3.1 Secondary endpoint(s)

#### 3.3.1.1 Definition of endpoint(s)

The 9-hole peg test (9-HPT) is a brief, standardized, quantitative test of upper extremity function (lower bound: 10 sec; upper bound: 300 sec). Two consecutive trials with the dominant hand are immediately followed by two consecutive trials with the non-dominant hand. The total time to complete the task is recorded. An increase of >20% from the baseline in the 9-HPT is considered meaningful worsening (4). To transform the data so that higher Z-scores correspond to an improved outcome and lower Z-scores correspond to deterioration, the inverse of the test values are taken prior to computing the Z-score. The baseline mean and standard deviation of all participants are used to create Z-scores:

$$Z = \frac{\frac{1}{2} \left( \frac{1}{trialarm, left} + \frac{1}{trialarm, right} \right) - Baseline Mean}{Baseline SD}$$

The times from the two trials for each hand are averaged, converted to the reciprocals of the mean times for each hand and then the two reciprocals are averaged, for example,

$$\frac{1}{trialarm, left} = \frac{1}{average of the two times of the left arm trails}$$

In case one of the two times for the same arm is missing, the available time will be used. In case 9-HPT was assessed for only one hand for reason other than "physical limitation", then the Z-score will be set to missing. For a participant who could not complete the 9-HPT due to a "physical limitation", the maximum time (300 sec) will be used. Missing values for other reasons will not be imputed. In case of values below (above) the lower (upper) bound, the value will be set to the respective bound.

The Timed 25-Foot Walk (T25-FW) test is a quantitative mobility and leg function performance test based on a timed 25-foot walk; time in seconds to walk 25 feet (lower bound: 2.2 sec; upper bound: 180 sec). For each assessment, 2 trials are performed. The score is the average of the times from the 2 trials (or single score if only 1 completed). An increase of >20% from baseline in the T25-FW test is considered meaningful worsening (4). The baseline mean and SD of all participants are used to create Z-scores:

$$Z = (-1) \times \frac{Average \ score - Baseline \ Mean}{Baseline \ SD}$$

The negative of the Z-score is used so that improvement is a positive number and worsening a negative number. For a participant who could not complete the 25-FW due to a "physical limitation", the maximum time (180 sec) will be used. Missing values for other reasons will not be imputed. If results from both trials are missing due to reasons other than "physical limitation", the Z-score will be set to missing. In case of values below (above) the lower (upper) bound, the value will be set to the respective bound.

Time to onset of 3-month CDP is defined as the time from randomization to the onset of a sustained increase from baseline in EDSS score (of  $\geq 1.0$  point from the baseline EDSS score when the baseline score is  $\leq 5.0$ , of  $\geq 0.5$  points when the baseline EDSS score is >5.0) confirmed after a minimum 3-month interval. The confirmation of 3-month CDP follows the same criteria as that of 6-month CDP.

Note: 3-month confirmation must be  $\geq$ 70 days after onset. Given that visits are scheduled every 12 weeks with a time window of  $\pm$  7 days for conducting EDSS assessment, the minimum per protocol allowed time between 2 EDSS assessments scheduled 12 weeks apart is 70 days (3 months = 12 weeks = 84 days minus a 7-day window for each of the 2 visits, ie, 84 - 14 = 70).

Confirmed disability improvement is defined as a  $\geq 1$  point decrease from baseline in the EDSS score lasting at least 6 months.

Symbol Digit Modalities Test (SDMT) is used to assess processing speed, divided attention, visual scanning, tracking and motor speed. The number of correct substitutions and number of items completed within a 90 second interval (max = 110) are recorded. A decrease of 4 points from baseline on the SDMT is considered meaningful worsening (5). The baseline mean and standard deviation of all participants are used to create the Z-score for SDMT number of correct substitutions:

$$Z = \frac{SDMT \ score - Baseline \ Mean}{Baseline \ SD}$$

Z-scores will be used for analysis.

The California Verbal Learning Test®-II (CVLT-II) is a verbal learning and memory test. It consists of recall and recognition of a list of 16 words. For each assessment, 5 trials are completed. The total correct, total intrusions, and total repetitions across the 5 trials combined are recorded and converted to a standardized score by sex within each of 7 age groups (6). Total Correct Recall Trials 1–5 is scaled to a normalized T-score metric, which has a mean of 50 and SD of 10, with higher values indicating better performance. Total intrusions and total repetitions are normed on a linear Z-score metric, with a mean of 0, SD of 1.0, and increment values of plus or minus 0.5. Higher positive Z-scores on these measures reflect greater deficits. Standardized scores will be used for analysis.

Multiple Sclerosis Quality of Life-54 (MSQoL-54) is a multidimensional health-related quality of life measure that combines both generic and MS-specific items into a single instrument (7). The recall time, when relevant, is for the previous 4 weeks. It is composed of 54 items. There are 2 derived summary scores, physical health composite and mental health composite, 12 subscale scores: physical function, role limitations-physical, role limitations-emotional, pain, emotional wellbeing, energy, health perceptions, social function, cognitive function, health distress, overall quality of life, and sexual function, and 2 single-item measures: satisfaction with sexual function and change in health. The total number of items in each subscale is listed as the divisor for each subtotal. Due to missing data, the divisor can be less than that if not every item within a given scale has been answered. Each subscale score can then be calculated by summing the non-missing item responses and dividing by the number of non-missing item responses. Physical health

composite score is calculated as a weighted sum of physical function (weight = 0.17), health perceptions (weight = 0.17), energy (weight = 0.12), role limitations-physical (weight = 0.12), pain (weight = 0.11), sexual function (weight = 0.08), social function (weight = 0.12) and health distress (weight = 0.11). Mental health composite score is calculated as a weighted sum of health distress (weight = 0.14), overall quality of life (weight = 0.18), emotional well-being (weight = 0.29), role limitations-emotional (weight = 0.24) and cognitive function (weight = 0.15). All scores are transformed linearly to a common 0 (worst) to100 (best) score range.

### 3.3.1.2 Main analytical approach

#### 3.3.1.2.1 Time to event endpoints

Time to onset of 3-month CDP will be analyzed using the same statistical methods as for the primary analysis of time to onset of 6-month CDP without imputation.

Time to onset of sustained 20% increase in the 9-HPT (T25-FW) for at least 3 months and time to onset of 6-month confirmed disability improvement (CDI) will be analyzed using similar statistical methods as for the primary analysis of time to onset of 6-month CDP, but without imputation. Participants with onset without confirmation will be treated as censored at the last endpoint assessment.

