9.4.3 Secondary endpoint(s)

For other time-to-event endpoints (time to onset of sustained 20% increase in the 9-HPT, of sustained 20% increase in the T25-FW, of 3-month CDP, and of CDI), similar analysis as for the primary analysis of the primary efficacy endpoint will be performed in the ITT population but without imputation.

Continuous endpoints (percent change in brain volume loss, change in cognitive function, change in physical function, and change in MSQoL-54 at EOS) will be analyzed using a mixed-effect model with repeated measures (MMRM) approach. The model will include change/percent change values for the respective endpoint at each scheduled visit as response variables, and treatment, age at screening (>40, \leq 40 years), geographic region (US, non-US), visit, treatment by-visit interaction, baseline value for the endpoint being assessed and baseline value-by-visit interaction as covariates. Difference in LS means, the corresponding 95% CI, and p-value will be provided for the comparison of SAR442168 versus placebo. For percent change in brain volume loss, log transformation will be applied in the MMRM model. In order to assess the impact of deviation from the normality assumption, a sensitivity analysis using rank ANCOVA with the same covariates as for the MMRM analysis except visit and related interaction terms, will be performed for these continuous endpoints to provide the p-value for the comparison between the treatment groups.

Categorical efficacy endpoints with count data (new and/or enlarging T2 hyperintense over the study period after baseline) will be analyzed using a negative binomial regression model. The model will include the total lesion count across all post-randomization MRI scans during the study period as the response variable, with treatment group, age at screening (>40, \leq 40 years), geographic region (US, non-US), baseline EDSS score, and baseline T2 lesions as covariates. Log-transformed observation duration from screening MRI to last available MRI will be the offset variable. In order to assess the impact of open-label therapy, sensitivity analysis excluding the data after initiation of open-label therapy will be performed for the key secondary endpoints that will be pre-specified in the SAP. Further details including details of missing data handling and subgroup analyses for secondary endpoints will also be detailed in the SAP.

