Change from baseline in SDMT number of correct substitutions, CVLT-II total correct and MSQoL-54 physical and mental health composite scores at the EOS will be analyzed using an analogous MMRM approach in the ITT population with the change from baseline values for the respective endpoint at scheduled visits up to and including the EOS visit as response variables, and treatment group, age at screening (>40,  $\leq$ 40 years), geographic region (US, non-US), visit, treatment-by-visit interaction, baseline value for the endpoint being assessed and baseline value-by-visit interaction as covariates.

For each endpoint, difference in LSM, the corresponding 95% CI, and p-value will be estimated from the MMRM model for the comparison of tolebrutinib to placebo using weights for each stratum equal to the overall proportion of participants in each stratum (ie, "Population weight"). Plots of LSM [±standard error (SE)] over time will be provided. Participants who discontinue study intervention before the study end will be asked and encouraged to return for all remaining study visits and the additional off-treatment values measured up through the EOS will be included in the primary analysis. For participants who withdraw from the study before the EOS, values will be missing after study discontinuation and no imputation will be performed.

SDMT, CVLT-II and MSQoL-54 data are assumed a priori to be normally distributed. Given the large sample size, the impact of violation of normality should not be great. In order to assess the impact of deviation from the normality assumption, a sensitivity analysis using rank analysis of

covariance (ANCOVA), with the same covariates as for the MMRM analysis except VISIT and related interaction terms, will be performed to test the significance of the treatment effect.

Given that participants who reach the primary endpoint of 6M-CDP are eligible to switch to OL tolebrutinib, including data after the switch could impact the analysis of secondary endpoints: number of new/enlarging T2 lesions per year, time to onset of sustained 20% increase in the 9-HPT (T25-FW) for at least 3 months, and percent change in brain volume at EOS compared to Month 6. Sensitivity analyses excluding data after initiation of OL therapy will be performed for these endpoints.

No other sensitivity, supplementary, or subgroup analyses will be performed for the secondary endpoints.

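### The 9-HPT and T25-FW Cox models, read literally, do not adjust for the test's own baseline; listing and adding it may recover some power at almost no cost

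*SAP*

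**What the plan says.** SAP 3.5 places time to sustained 20% increase in the 9-HPT and in the T25-FW third and fourth among the secondary endpoints of the hierarchy. CDI and percent change in brain volume follow them.

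SAP 3.3.1.2.1 says that these two endpoints and CDI "will be analyzed using similar statistical methods as for the primary analysis of time to onset of 6-month CDP, but without imputation". For 3-month CDP, the same section says that it "will be analyzed using the same statistical methods as for the primary analysis of time to onset of 6-month CDP without imputation". Protocol 9.4.3 uses one phrase for all four: "similar analysis as for the primary analysis of the primary efficacy endpoint will be performed in the ITT population but without imputation".

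The primary model is in SAP 3.2.2: "The covariates included in the model are treatment group, age at screening", followed by region, baseline EDSS score and baseline Gd-enhancing T1 lesion status. Neither document names baseline 9-HPT or baseline T25-FW as a covariate.

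The events are defined against that baseline in SAP 3.3.1.1: "An increase of >20% from the baseline in the 9-HPT is considered meaningful worsening" and "An increase of >20% from baseline in the T25-FW test is considered meaningful worsening". The schedule in Protocol 1.3 has both tests performed at the randomization visit.

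**The concern.** The two models take over a covariate list built for an EDSS endpoint. For 6-month CDP, baseline EDSS is the endpoint's own baseline. For 9-HPT and T25-FW it is the baseline of a different scale. No reason is given for treating these two tests differently from the rest of the hierarchy.

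Leaving a prognostic covariate out of a Cox model pulls the estimated hazard ratio toward 1 and costs power. Under fixed-sequence testing, a miss on 9-HPT stops formal testing of T25-FW, CDI and brain volume, and a miss on T25-FW stops the last two.

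There is also a question of wording. The SAP writes *same* methods for 3-month CDP but only *similar* methods for 9-HPT, T25-FW and CDI, so the covariate set of two confirmatory models is left to inference.

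**Working it through.** **1. Own starting value in each confirmatory model**

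| Test, in order | Own starting value in the model? | Where in the SAP |
|---|---|---|
| 6-month CDP (primary) | yes, baseline EDSS | 3.2.2 |
| 3-month CDP | yes, baseline EDSS | 3.3.1.2.1 |
| New/enlarging T2 lesions | yes, baseline T2 count | 3.3.1.2.2 |
| 9-HPT, 3-month | not listed | 3.3.1.2.1 |
| T25-FW, 3-month | not listed | 3.3.1.2.1 |
| CDI | yes, baseline EDSS, through the primary list | 3.3.1.2.1 |
| Brain volume | yes, Month 6 volume | 3.3.1.2.3 |

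The MMRMs for SDMT, CVLT-II and MSQoL-54 also include the "baseline value for the endpoint being assessed".

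**2. The plan's own figure**

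SAP 4 gives about 288 events for 80% power at HR 0.70, two-sided 5%, 2:1 allocation. This is for 6-month CDP; nothing similar is stated for 9-HPT or T25-FW.

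- Schoenfeld events: (1.960 + 0.842)² / [(1/3)(2/3)(ln 0.70)²] = 7.849 / 0.02827 = 278. Power at 288 events: Φ(√(288 × 0.02827) − 1.960) = Φ(0.893) = 81.4%.
- Exponential rate-difference formula with unpooled variance: a 2-year placebo rate of 23.6%, 10% yearly dropout and 24 + 24 months give event probabilities of 0.2852 (placebo) and 0.2109 (active). With hazards in ratio 1 to 0.7, N = 7.849 × [1/(0.2852/3) + 0.49/(0.2109 × 2/3)] / 0.3² = 1221. Events = 1221 × (0.2852/3 + 0.2109 × 2/3) = 287.8.

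The 288 reproduces. It does not depend on the present point.

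**3. Power with and without the test's baseline, if baseline acts directly on the hazard**

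From the documents: N = 1290, 2:1, 10% yearly dropout, 24 + 24 months. Borrowed from the primary endpoint as an assumption: HR 0.70 and a 23.6% 2-year placebo rate. Assumed with no source in the documents: the hazard ratio per SD of log baseline, and its correlation with baseline EDSS. Both models contain treatment and EDSS. EDSS affects the hazard only through the correlation. There were 1000 runs per cell, with a Monte Carlo SE of about 1.0 to 1.5 points per power.

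| HR per SD | Correlation 0: without → with | Gain | Correlation 0.5: without → with | Gain |
|---|---|---|---|---|
| 1.0 | 86.3 → 86.0% | −0.3 | 85.5 → 85.6% | 0.1 |
| 1.25 | 85.0 → 85.6% | 0.6 | 86.9 → 87.1% | 0.2 |
| 1.5 | 84.6 → 85.3% | 0.7 | 84.7 → 87.3% | 2.6 |
| 2.0 | 82.1 → 88.8% | 6.7 | 85.1 → 89.7% | 4.6 |
| 2.5 | 79.3 → 89.6% | 10.3 | 81.3 → 89.3% | 8.0 |

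At correlation 0, the fitted hazard ratio without the covariate was 0.707 at HR per SD 1.5, 0.721 at 2.0 and 0.742 at 2.5, against 0.700 to 0.703 with it. With a 15% placebo rate the gains were 0 to 2.3 points up to 1.5, 4.8 at 2.0, and 7.7 to 11.1 at 2.5. A separate simulation at HR 0.75 and a 20% placebo rate (also assumptions) gave gains of 0.5 and 1.3 points at HR per SD 1.3, 2.9 and 2.6 at 1.6, and 7.1 and 5.4 at 2.0, for correlations 0.3 and 0.6.

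**4. Power when events come from the 20% rule**

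Test times were generated every 3 months with measurement error, and an event was a 20% rise sustained at the next visit. Twelve settings varied the baseline spread, the error and the link between baseline and rate of worsening (all assumed), with 300 runs each. The hazard ratio per SD of observed baseline ran from 0.66 to 1.55. Adding baseline changed power by −2 to +2 points, which is within simulation noise.

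**The case against.** The strongest reply is that no loss has been shown. The threshold is a percentage, so it already scales with baseline. A high first reading tends to be followed by lower ones, which can offset faster worsening in people who start worse. Step 4 bears this out: even the sign of the association is uncertain there. Step 3 shows a clear gain only because it gives baseline a strong direct effect. This stands, and it limits the claim to a possible gain.

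Second, *similar* does not exclude the covariate. A reader might infer that the SAP rules it out; the text only fails to list it. That stands too, but a confirmatory model should not depend on the reading of one word.

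Third, the covariate set looks deliberate. The SAP version history records that EDSS and Gd status were specified for the primary and related time-to-event endpoints on clinical input, and a common set keeps the hazard ratios on similar conditioning. EDSS also includes ambulation scoring (Protocol 8.1.1), so it may already carry walking information for the T25-FW. This is fair, but it does not explain why these two tests alone lack their own baseline.

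Fourth, SAP 3.3.1.1 caps 9-HPT at 300 s and T25-FW at 180 s. A participant starting at or above 300/1.2 = 250 s or 180/1.2 = 150 s cannot exceed a 20% rise, so a single linear log-baseline term may fit poorly at the top of the scale. How many participants this concerns is unknown. It may reduce the gain; it does not make the treatment comparison invalid.

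Fifth, the change is not entirely free. A Cox fit drops anyone with a missing covariate, and SAP 3.3.1.1 does not impute tests missing for reasons other than physical limitation. This stands and is met in the fix.

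**Conclusion.** The point holds as a low-cost improvement and a gap in specification. Read literally, the two models leave out the test's own baseline, while the other five tests in the hierarchy adjust for theirs.

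The power at stake is about 0 to 3 points for a hazard ratio per SD of baseline up to about 1.5 and about 5 to 7 points at 2.0. It may be nil, as when events follow the 20% rule directly. These sizes rest on assumed prognostic strength, correlation with EDSS, event rate and treatment effect, none of which the documents give for 9-HPT or T25-FW.

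A reader might infer that the plan definitely gives up power, or that these two tests are biased in a way that threatens error control. The documents support neither. The treatment comparison is randomized, Type I error is unaffected, and the size of any loss cannot be fixed from the documents.

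**What to change.** Before unblinding, amend SAP 3.3.1.2.1:

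- List the covariates of the 9-HPT and T25-FW Cox models explicitly: treatment, age group, region, baseline EDSS, baseline Gd status, and the log-transformed baseline time of the test being analysed.
- Make the same addition for the 6-month sustained versions in SAP 3.4.2.
- Add a short rule for a missing baseline test, so that no ITT participant is dropped from the fit. SAP 3.1 already does this for baseline Gd status. One option is to use the mean log baseline of the overall population, for the covariate only.

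The cost is one degree of freedom in each model and the missing-baseline rule. The schedule already collects both tests at randomization, so no new data are needed, and the endpoint definitions and testing order do not change.
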